**8.2.4 Time period and frequency for event assessment and follow-up**

The occurrence of a treatment emergent adverse event (TEAE) or serious adverse event (SAE) may come to the attention of study personnel during study visits or other contacts with participants or communication from other medical providers caring for the study participant. All non-serious TEAEs will be followed up until satisfactory resolution or the child completes participation in week 9 of the study. All SAEs will be followed until satisfactory resolution or until the site investigator deems the event to be chronic or the participant is stable.

---

**8.2.5 Adverse event reporting**

All AEs not meeting the criteria for SAEs will be captured in the through a general AE inquiry. Information to be collected initially includes event description, clinician's assessment of intensity, relationship to study procedures (note NO study medication provided). If the event has resolved that will also be collected. AEs will be followed to adequate resolution or the completion of the child's week 9 visit in the study. Any medical condition that is present at the time that the participant is screened or at the week 0 visit will be considered as past medical history and not reported as a treatment emergent AE unless there is a significant increase in the condition's intensity leading to a change in the intensity rating.

---

**8.2.6 Serious ADVERSE EVENT REPORTING**

An SAE is defined as an AE that meets certain conditions as defined in section 8.3.2. As soon as study staff become aware of a possible SAE, they will notify the study physician and study PI.

The study physician or PI will review and evaluate the potential SAE, obtaining external medical records if possible.

If the event is deemed to be an SAE:

- The ACE Center PIs will be notified within 24 hours.
- Record event in a NTF

- The study clinician (MD) will follow the trajectory of the SAE until it is resolved or deemed to be clinically stable or for 1 month following the week 16 visit.

Timeline for reporting of SAEs is:

- DSMB: The PI will report SAEs that are considered possibly related to study treatment to the DSMB within 14 days of being made aware of their occurrence.
- IRB: SAEs will be reported to the IRB in the context of the annual report or within 14 days of being made aware of the SAE's occurrence if it is considered related and unexpected or results in death.
- NICHD: The ACE center co-PIs and study PI will report SAEs that result in death to the NICHD program officer within 48 hours of becoming aware of the event, regardless of whether the SAE was related or expected. If SAE does not result in death or permanent disability, but is considered related and unexpected, we will report it to the NICHD program officer within 14 days of becoming aware of the SAE. SAEs that are not considered related or unexpected will be reported in annual progress reports.

---

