# 7 STUDY INTERVENTION DISCONTINUATION AND PARTICIPANT WITHDRAWAL

## 7.1 Study Halting Rules

The DSMB may choose to halt the study at any time they feel there is significant risk to participants as a result of study procedures or as a result of the study behavioral treatment (ESDM-informed caregiver coaching), or of specific study assessments. Since the behavioral treatment is well accepted in the community and does not appear to have specific safety concerns and the assessments are used in a wide variety of studies of young children with ASD and have never been shown previously to result in significant safety risks we expect there will be very low risk for study halting due to safety concerns.

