### 8.3.1 Definition of unanticipated problems (UP)

The Office for Human Research Protections (OHRP) considers unanticipated problems involving risks to participants or others to include, in general, any incident, experience, or outcome that meets **all** of the following criteria:

- Unexpected in terms of nature, severity, or frequency given both the research procedures that are described in the protocol-related documents, and the characteristics of the participant population being studied;
- Related or possibly related to participation in the research and
- Suggests that the research places participants or others at a greater risk of harm (including physical, psychological, economic, or social harm) than was previously known or recognized.

---

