### 8.3.2 Unanticipated problem (UP) reporting

The UP report will include the following information:

- Protocol identifying information: protocol title and number, PI's name, and the IRB project number;
- A detailed description of the event, incident, experience, or outcome;
- An explanation of the basis for determining that the event, incident, experience, or outcome represents an UP;
- A description of any changes to the protocol or other corrective actions that have been taken or are proposed in response to the UP.

Timelines for reporting the UP are listed below. The FDA and IRB require different reporting based on the characteristics of the UP as noted below.

- Study PI within 24 hours of staff suspecting a UP
- ACE Center co-PIs within 7 days of the Study PI confirming a UP has occurred.
- DSMB: The ACE co-PIs and the study PI will report UPs that are considered possibly related to study treatment to the DSMB within 14 days of being made aware of their occurrence.
- IRB: The PI is responsible for reporting unanticipated problems according to the time frames below.
  - Unanticipated Problems that are also SAEs within 7 days of becoming aware of the event.
  - Any other Unanticipated Problem within 14 days of becoming aware of the problem.

---

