## 8.4 Overall Plan to Protect Patient Safety

**Data Safety and Monitoring Board (DSMB)** The study will have a three-person data and safety monitoring board that reviews the initial protocol prior to any participant being enrolled. After the first participant has enrolled and started the study, until the last participant has completed the week 16 visit, the DSMB will meet a minimum of two times a year to review the study's progress and the safety. Specifically, the following will be reviewed at each meeting:

1. enrollment as compared to proposed enrollment,
2. SAEs and UPs with any resulting changes in study procedures or consents,
3. participant discontinuation, study withdrawals, and study completions
4. adverse events separated by system organ class, severity and relatedness,
5. protocol deviations

The membership of the DSMB includes two child psychiatrists who are experts in psychopharmacological treatments for ASD and conducting clinical trials in ASD and a statistician. The DSMB will determine at each meeting whether there are any concerns, especially with regard to safety, that lead the board to conclude that the study should be suspended or that the protocol should be amended to provide greater protections for subjects. The DSMB may also raise concerns or provide suggestions to improve recruitment or procedures for the trial.

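### A death judged unrelated to study treatment goes promptly to NICHD and the IRB but has no expedited route to the DSMB, and the DSMB's reporting triggers are narrower than its power to halt

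*Combined protocol and SAP*

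**What the plan says.** Section 8.2.6 sets a separate reporting time for each of three bodies.

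- **DSMB:** the PI reports "SAEs that are considered possibly related to study treatment to the DSMB within 14 days" of being told of them. Death is not mentioned.
- **IRB:** an SAE goes in the annual report, or within 14 days "if it is considered related and unexpected or results in death".
- **NICHD:** an SAE resulting in death is reported "within 48 hours of becoming aware of the event, regardless of whether the SAE was related or expected". Non-fatal SAEs that are related and unexpected go within 14 days, and the remainder in annual progress reports.

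The study physician or the PI evaluates each potential SAE.

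For unanticipated problems (UPs), 8.3.1 requires that the event be "Related or possibly related to participation in the research". The DSMB line in 8.3.2 then covers only "UPs that are considered possibly related to study treatment to the DSMB within 14 days of being made aware of their occurrence".

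On the board's powers, 7.1 says: "The DSMB may choose to halt the study at any time they feel there is significant risk to participants as a result of study procedures". It goes on to name the coaching intervention and specific assessments as further grounds. On timing, 8.4 says that "the DSMB will meet a minimum of two times a year to review the study's progress and the safety", and lists SAEs and UPs among the items for every meeting, with no filter on relatedness. The Safety oversight section (10.1.1) states that the board is independent of the university and of the study.

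**The concern.** The plan treats a death as urgent in its own right for the funder and for the IRB, but not for the independent board that can stop the study. Whether that board hears promptly of a death depends on a causality call by the team it oversees.

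The second part is a mismatch of scope. Section 7.1 gives the board three distinct sources of risk to act on: procedures, the behavioral treatment and assessments. The two expedited lines that feed it name only treatment. An event linked to an assessment is within the board's remit but outside its prompt reports.

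At stake is how soon the board can form its own view on relatedness and on whether the study should continue.

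**Working it through.** There is no sample size, power or event count to reproduce here. The check sets the reporting routes side by side and then sizes the possible delay.

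**Step 1. Routes by type of event** (8.2.6, 8.3.1, 8.3.2, 8.4). Non-fatal rows exclude permanent disability, for which 8.2.6 gives NICHD no time of its own.

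| Event | DSMB | IRB | NICHD |
|---|---|---|---|
| Death, judged unrelated to treatment | next scheduled meeting | 14 days | 48 hours |
| Death, possibly related to treatment | 14 days | 14 days (7 if also a UP) | 48 hours |
| Non-fatal SAE, possibly related to treatment, expected | 14 days | annual report | annual report |
| Non-fatal SAE, unrelated | next scheduled meeting | annual report | annual report |
| Non-fatal SAE that is a UP, linked only to an assessment | next scheduled meeting | 7 days | 14 days |

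In the IRB line, the verb structure makes death a trigger of its own, so relatedness is not needed for a fatal event.

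**Step 2. Is there another early route to the DSMB?** The UP route does not catch an unrelated death, because 8.3.1 requires possible relation to the research. Nor does it catch a UP linked only to an assessment, because the DSMB line in 8.3.2 repeats the treatment condition. Section 10.1.6 allows earlier notice to the DSMB, but of protocol deviations with safety concerns. Section 8.2.7 concerns what caregivers are told. Safety oversight refers back to 8.4. No other early route appears in the text available; 10.1.2 Key roles and study governance and the opening of 10.1.3 Clinical data monitoring were not available to check.

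**Step 3. Possible wait for an unrelated death.** Input: at least two meetings a year (8.4). Spacing is not stated, so even spacing is an assumption.

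- Longest wait with two meetings: 52 / 2 = 26 weeks, or 26 × 7 = 182 days.
- Average wait, if the event is equally likely at any time between meetings: 26 / 2 = 13 weeks.
- Longest wait with four evenly spaced meetings: 52 / 4 = 13 weeks.
- With two unevenly spaced meetings the longest wait would exceed 26 weeks.

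The comparison is 14 days for the IRB and 48 hours for NICHD. At the two-meeting minimum, the longest wait is 182 / 14 = 13 times the IRB's limit.

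**The case against.** The strongest reply is that the DSMB is not generally the worse-informed body. Step 1 shows this for non-fatal SAEs: the DSMB trigger asks only for possible relation and sets no condition of unexpectedness, so a possibly related but expected SAE reaches the board in 14 days and the IRB only in the annual report. Unrelated non-fatal SAEs reach the board at least twice a year. This stands. A reader might infer that all serious events judged unrelated bypass the DSMB relative to the other bodies; the documents support that contrast for deaths only.

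Nor are events hidden from the board. Under 8.4 it sees every SAE and UP at each meeting, and adverse events by severity and relatedness, so it can question the team's causality calls. Two meetings is a floor. This also stands, and it limits the point to timing.

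A reader might multiply the wait by the planned accrual of 1-3 participants a month and present the result as children put at risk. That would count ordinary enrolment. Nothing in the documents shows that a death judged unrelated raises the risk to later participants, or that the board would have halted.

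On assessments, the tasks are mainly questionnaires, interviews, a six-minute play recording and an app, and 2.4.1 puts their risk at the level of daily life. An SAE caused by one is unlikely. *Study treatment* may also be loose drafting, since the adverse event form records relatedness to study procedures (8.1, 8.2.5). But 7.1 lists the terms separately, and 8.3.2 repeats the narrow term directly after a wider definition in 8.3.1. The mismatch is real, though its practical weight is low.

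**Conclusion.** The point holds for deaths. As written, 8.2.6 lets a death judged unrelated to treatment reach the DSMB only at its next scheduled meeting. That could be up to about 26 weeks later, assuming exactly two evenly spaced meetings a year and an event just after one of them. This is what the text permits, not a forecast; the board may meet more often or be told informally.

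The treatment-only wording in 8.2.6 and 8.3.2 is a secondary inconsistency with 7.1 and 8.3.1. It should be reconciled but is not a demonstrated safety gap.

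The change is worth making because it costs almost nothing and the omission concerns the one independent body with authority to halt. In a study without study medication that is described as minimal risk, few such events are to be expected, and the point does not affect any endpoint or analysis.

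**What to change.** Reword the DSMB line in 8.2.6 so that it covers SAEs possibly related to study treatment, study procedures or study assessments, and any SAE resulting in death regardless of relatedness, reported within 14 days or sooner. In 8.3.2, replace treatment with treatment, procedures or assessments in the DSMB line.

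This leaves non-fatal SAEs judged unrelated to the scheduled meetings, which is reasonable given that the IRB and NICHD receive them only annually.

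The cost is a short protocol amendment. A death is already reported to NICHD and the IRB, so the extra work is copying that report to the DSMB. The wider trigger adds at most a few further reports. No study procedure, clinical rule or analysis changes.

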### 8.2.7 Reporting events to participants

If any information emerges that the DSMB or IRB concludes significantly changes the risk: benefit profile of participation in the study, the information will be incorporated into a revised informed consent document for approval by the IRB and the caregivers of participants who are still active in the study will be re-consented with IRB approved revised consent at the earliest possible opportunity.

---

### 8.2.8 Reporting of pregnancy

Not-applicable due to age of participants.

---

### 8.2.9 Reporting of suspected child abuse or neglect

If any member of the study staff has significant concerns that a participant may be being abused or neglected, they will discuss it with the study PI. The study PI will attempt to obtain any additional information felt necessary to clarify the situation. If after this there is still concern about abuse or neglect, the PI will contact Child Protective Services and file a report.

---

## 8.3 Unanticipated Problems

---

### 8.3.1 Definition of unanticipated problems (UP)

The Office for Human Research Protections (OHRP) considers unanticipated problems involving risks to participants or others to include, in general, any incident, experience, or outcome that meets **all** of the following criteria:

- Unexpected in terms of nature, severity, or frequency given both the research procedures that are described in the protocol-related documents, and the characteristics of the participant population being studied;
- Related or possibly related to participation in the research and
- Suggests that the research places participants or others at a greater risk of harm (including physical, psychological, economic, or social harm) than was previously known or recognized.

---

### 8.3.2 Unanticipated problem (UP) reporting

The UP report will include the following information:

- Protocol identifying information: protocol title and number, PI's name, and the IRB project number;
- A detailed description of the event, incident, experience, or outcome;
- An explanation of the basis for determining that the event, incident, experience, or outcome represents an UP;
- A description of any changes to the protocol or other corrective actions that have been taken or are proposed in response to the UP.

Timelines for reporting the UP are listed below. The FDA and IRB require different reporting based on the characteristics of the UP as noted below.

- Study PI within 24 hours of staff suspecting a UP
- ACE Center co-PIs within 7 days of the Study PI confirming a UP has occurred.
- DSMB: The ACE co-PIs and the study PI will report UPs that are considered possibly related to study treatment to the DSMB within 14 days of being made aware of their occurrence.
- IRB: The PI is responsible for reporting unanticipated problems according to the time frames below.
  - Unanticipated Problems that are also SAEs within 7 days of becoming aware of the event.
  - Any other Unanticipated Problem within 14 days of becoming aware of the problem.

---

### 8.3.3 Reporting unanticipated problems to participants

The informed consent document for the study will be revised to reflect the UP. After IRB approval of the revised informed consent document is received, all participants who are continuing to be treated within A+ Treatment will be reconsented. In addition, all participants who do not have a previously scheduled appointment within 2 weeks of the approval of the revised informed consent document will be notified by phone, email or mail that the UP has occurred and that a revised consent form now exists. They will be asked to contact study staff if they wish to discuss the event prior to the next scheduled study visit.

## 8.4 Overall Plan to Protect Patient Safety

**Data Safety and Monitoring Board (DSMB)** The study will have a three-person data and safety monitoring board that reviews the initial protocol prior to any participant being enrolled. After the first participant has enrolled and started the study, until the last participant has completed the week 16 visit, the DSMB will meet a minimum of two times a year to review the study's progress and the safety. Specifically, the following will be reviewed at each meeting:

1. enrollment as compared to proposed enrollment,
2. SAEs and UPs with any resulting changes in study procedures or consents,
3. participant discontinuation, study withdrawals, and study completions
4. adverse events separated by system organ class, severity and relatedness,
5. protocol deviations

The membership of the DSMB includes two child psychiatrists who are experts in psychopharmacological treatments for ASD and conducting clinical trials in ASD and a statistician. The DSMB will determine at each meeting whether there are any concerns, especially with regard to safety, that lead the board to conclude that the study should be suspended or that the protocol should be amended to provide greater protections for subjects. The DSMB may also raise concerns or provide suggestions to improve recruitment or procedures for the trial.

## 9 STATISTICAL CONSIDERATIONS

### 9.1 Sample Size Determination

Since this is a feasibility study not an efficacy trial, the sample size was determined based on expected ability to recruit during the period of the study.

### 9.2 Population for Analysis

The primary analysis population will include all participants.

The safety population will include all participants

### 9.3 Statistical Analyses

#### 9.3.1 General approach

We will conduct preliminary checks to identify potential outliers and missing data. We also will examine clinically meaningful subgroupings such as age, gender, and IQ. As part of the study design, efforts will be made to collect all outcomes on all participants, even when behavioral intervention is prematurely terminated.

A final statistical analysis plan will be developed and signed prior to final database lock.

### 9.3.2 Analysis of the primary efficacy endpoint

The primary feasibility analysis will focus on the Acceptability of Intervention Measure (AIM), Intervention Appropriateness Measure (IAM), and Feasibility of Intervention Measure (FIM). These measures can be administered to a wide range of stakeholders to determine the extent to which they believe an intervention or implementation strategy is acceptable, appropriate, and feasible. Readability is at the 5th grade level. Higher scores indicate greater acceptability, appropriateness, and feasibility. The AIM, IAM, and FIM have demonstrated content validity, discriminant content validity, reliability, structural validity, structural invariance, known-groups validity, and responsiveness to change. Means and standard deviations will be reported for the AIM, IAM, and FIM. Descriptive statistics on caregiver completion rates for the 8-session treatment program will be reported.

Acceptability, appropriateness and feasibility will also be assessed **qualitatively** with stakeholder individual interviews. In the field of implementation science, qualitative methods are frequently used to shed light on key implementation challenges. Questions in the interview guide will be tailored to stakeholder group (Caregivers, Coaches, Clinicians, or Staff) and will be informed by previous studies that have examined barriers and facilitators during the implementation of a new treatment approach. Interviews will be conducted with caregivers after they have completed coaching sessions and with coaches, clinicians, and staff once they have delivered the intervention and supported coaching activities for a 6-month period. Qualitative analysis will use an iterative coding and review process informed by grounded theory. To minimize bias and protect privacy, personal names and direct identifiers in transcripts of the interviews will be replaced with a code or descriptor. Qualitative data will initially be coded independently by two team members at a general level in order to condense data into analyzable units. Responses will be assigned codes based on a priori or emergent themes. Disagreements will be resolved by reviewing transcripts and additional discussion. A final list of codes will be developed through consensus. Axial coding will then be used to generate categories arranged in a tree-like structure connecting segments into separate nodes, describing the relationship between codes and subcategories. Nodes and trees will be used to create a taxonomy of themes including a priori, emergent and new categories. Qualitative coding will then be quantified using frequency counts to identify primary themes. Participant quotes from individual interviews will inform assessments of acceptability, appropriateness, and feasibility of the adapted coaching approach.

Fidelity of intervention delivery, the degree to which programs are implemented as intended by program developers, is an important implementation outcome because it can moderate the effect of an intervention on targeted health outcomes. When interventions are adapted to fit a new target population, delivery setting, location or organization, maintaining intervention fidelity is of particular importance. Fidelity of caregiver implementation of ESDM strategies will be assessed quantitatively, using an adapted version of the Parent Early Start Denver Model (P-ESDM) Caregiver Fidelity Rating System. The P-ESDM Caregiver Fidelity Scale provides a method for assessing the fidelity with which a caregiver is using ESDM principles in a joint activity routine with their young child. The 13 item rating scale includes ratings of performance from 1 to 5. Observations will be coded from video-recorded caregiver-child interactions completed at baseline (pre-intervention) and at 9-weeks (post-intervention), by certified ESDM therapists who are naïve with respect to whether they are coding the baseline or 9-week observation. Tabular and graphical summaries of pre and post caregiver implementation fidelity will be generated to assess the degree to which the average in the cohort changes over time. Inference on pre-post change will be based on paired t-tests or, if the assumptions are found to be untenable, the Wilcoxon signed rank test for paired samples.

---

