1.2 Schema

**Figure 1: A+ Treatment Schema** A+ Treatment staff will meet with parents/caregivers to explain the study and to review the informed consent document with them. Eligibility in the A+ Treatment study will include meeting diagnostic and age criteria. ESDM-informed caregiver coaching begins after baseline assessments and will continue for 8 weeks. The primary outcome assessments will evaluate feasibility of ESDM-informed caregiver coaching in children ages 3-10. This study will be conducted remotely.

Week -2 to -1	Week 0	Weeks 1-8	Week 9	Week 16
Screen & Confirm Diagnose	Baseline	ESDM Sessions	Endpoint	Remote Follow-up
Diagnostic assessments Cognitive testing Parent questionnaires Vineland-3 parent report	Joint engagement Social communication ADHD symptoms AIM Parent questionnaires	ESDM Caregiver Fidelity ESDM Caregiver Self-Monitoring ESDM Coaching Fidelity	Joint engagement Social communication ADHD symptoms AIM Qualitative interview Vineland-3 parent report Parent questionnaires	Social communication ADHD symptoms Parent Questionnaires Vineland-3 parent report

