#### 4.4 End of Study Definition

A participant is considered to have completed the study if he or she has completed the endpoint assessments of all phases of the study or has been withdrawn from both treatment and assessments in the study. If a participant chooses to stop behavioral treatment in the study before endpoint assessments, he or she will be requested to complete them on schedule if at all possible. The follow-up visit at 16 weeks following baseline is optional.

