**Rationale for Selection Criteria:** We have included children between 36 months and < 132 months of age in order to facilitate recruitment. We excluded children below 36 months' chronological age in order to ensure that ADHD can be reliably diagnosed. We are allowing additional comorbid diagnoses or symptoms because studies suggest that a substantial percentage of children with ASD+ADHD will have a third psychiatric diagnosis or other symptoms, and we would not be able to reach our recruitment goals if these children were excluded. Additionally, the study will not exclude participants solely on the basis of a known genetic or neurological condition, as this would unnecessarily prevent otherwise eligible children with ASD and ADHD from participating in and potentially benefiting from this intervention. Furthermore, behavioral intervention is not anticipated to pose an additional risk due to these characteristics; inclusion will also allow for a more representative sample. Participants may be found ineligible if, according to study clinician judgment, it is not in the best interests of the participant and/or the study for the child to participate (including presence of psychiatric conditions or psychiatric symptoms in addition to ASD and ADHD that in the opinion of the PI or based on senior clinical review, would confound assessments and/or affect participation in the study). All children will be administered the Child Behavior Checklist (CBCL), which is a widely-used, well-normed, and empirically validated tool to facilitate diagnosis of other psychiatric problems. If a child has clinically elevated scores, this will be followed up with a semi-structured diagnostic interview by an expert clinician.

**Attrition:** We conservatively estimate that ~15% will not be able to meet the time, technology demands of the study.

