## 8 STUDY ASSESSMENTS AND PROCEDURES

- **Acceptability of Intervention Measure (AIM), Intervention Appropriateness Measure (IAM), and Feasibility of Intervention Measure (FIM).** (Weiner et al., 2017) These measures have been administered to a wide range of stakeholders to determine the extent to which they believe an intervention or implementation strategy is acceptable, appropriate, and feasible. Readability is at the 5th grade level. Higher scores indicate greater acceptability, appropriateness, and feasibility. The

AIM, IAM, and FIM have demonstrated content validity, discriminant content validity, reliability, structural validity, structural invariance, known-groups validity, and responsiveness to change. This measure will be completed with participants who enroll in the study, as well as coaches, clinicians, and support staff who consent to conduct the Qualitative Interview and AIM-IAM-FIM survey.

- **Two Early Start Denver Model (ESDM) fidelity scales will be utilized in this study:** (1) ESDM Coaching Fidelity Rating System; and the (2) Parent Early Start Denver Model (P-ESDM) Caregiver Fidelity Rating System. The ESDM Coaching Fidelity Rating System evaluates 14 coaching behaviors during the caregiver coaching sessions. Items are individually rated with a Likert-type rating scale with values that vary from 1 to 4, with higher scores reflecting a greater degree of fidelity. A portion of the items evaluate specific activities within the intervention session (e.g., warm-up activity, coaching on the topic) and the remaining items assess coaching characteristics which are evaluated across the entire session (e.g., reflective, nonjudgmental). The P-ESDM Caregiver Fidelity Scale provides a method for assessing the fidelity with which a caregiver is using ESDM principles in a joint activity routine with their young child. The 13 item rating scale includes ratings of performance from 1 to 3.

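### Caregiver interviews are described only for after coaching is completed, with no stated route for families who stop early, so acceptability and feasibility may be overstated if those families do not respond

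*Combined protocol and SAP*

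**What the plan says.** The primary endpoint combines the AIM, IAM and FIM scales, stakeholder interviews and fidelity ratings (Section 1.1).

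- **Interviews.** Section 9.3.2 states: "Interviews will be conducted with caregivers after they have completed coaching sessions". The interview entry in Section 8 says the same. The Schedule of Activities (Section 1.3) marks the interview once, under the week-9 endpoint assessments.
- **Scales.** The Schedule marks AIM, IAM and FIM once, also at week 9. The schema in Section 1.2 lists AIM in its week-0 column as well: "Joint engagement Social communication ADHD symptoms AIM Parent questionnaires".
- **Expected loss.** Section 5.5: "We conservatively estimate that ~15% will not be able to meet the time, technology demands of the study". The target there is 30 to 35 children; Section 5 gives 35.
- **Early stoppers.** Section 4.4 says that a participant who stops coaching before the endpoint assessments is to be asked for them: "he or she will be requested to complete them on schedule if at all possible". Section 9.3.1 promises efforts to obtain every outcome even after coaching ends early. Section 7.4 has staff encourage the final assessment when they can reach a caregiver who missed visits. Section 9.2 takes all participants as the primary analysis population.
- **Respondents and summary.** Section 8 has enrolled participants complete the scales, "as well as coaches, clinicians, and support staff who consent to conduct the Qualitative Interview and AIM-IAM-FIM survey". The planned summary is: "Means and standard deviations will be reported for the AIM, IAM, and FIM". Section 9.3.2 also reports completion rates for the eight sessions.

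**The concern.** Families who leave because remote coaching took too much time or technology hold direct evidence on feasibility. Read literally, the interview sentence leaves them out. Section 9.3.2 then counts how often themes occur to identify the primary ones, so barriers that made families stop would not be counted from the caregivers who met them.

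For the scales, the risk is selective non-response. The only time point in the Schedule is week 9, which may be weeks after a family has left. The provisions for reaching such families are requests and efforts. Section 7.3 also lets an investigator withdraw a participant from the study for significant non-compliance with the intervention, which could remove some of these families before week 9. The plan gives no method for primary scores that are still missing.

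Section 2.3 says the project is meant to inform the design of a later combination trial. If early stoppers are under-represented, that trial would be designed on a more favourable account than enrolled families would have given.

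**Working it through.** **Plan's own figure.** There is none to reproduce. Section 9.1 sets the sample size by recruitment capacity, and no precision target or success threshold is given for the scales.

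**Passages side by side.** Sections 8 and 9.3.2 place the caregiver interview after completed coaching. The Schedule places it at the endpoint visit, and Sections 4.4 and 9.3.1 seek endpoint data from those who stopped. A coordinator following Sections 8 and 9.3.2 could skip a stopper; one following Section 4.4 would invite the same caregiver. The scales are tied to a visit, not to completion, so the same conflict does not arise for them.

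**Families concerned.** 0.15 × 30 = 4.5 and 0.15 × 35 = 5.25, so roughly 5.

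**Effect on a caregiver mean.** Let d be the share who stop early (0.15, from Section 5.5), r the share of stoppers who answer, and D the amount by which completers score above stoppers, in SD. The documents give neither r nor D, so both are assumed over a range. It is also assumed that all completers answer and that stoppers who answer resemble those who do not. Set the completers' mean to 0:

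- mean over all enrolled = −dD
- observed mean = −drD / ((1 − d) + dr)
- bias = observed − all enrolled = dD − drD / ((1 − d) + dr)

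For D = 1 and r = 0.5: 0.15 − 0.075/0.925 = 0.15 − 0.081 = 0.069.

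| Gap D (SD) | None answer | Half answer | All answer |
|---|---|---|---|
| 0.5 | 0.075 | 0.034 | 0 |
| 1.0 | 0.150 | 0.069 | 0 |
| 1.5 | 0.225 | 0.103 | 0 |

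With D = 1 and no stopper answering, 5% attrition gives 0.05 SD and 25% gives 0.25 SD.

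**Against sampling error.** The 95% half-width for a mean is 1.96/√30 = 0.36 SD at n = 30 and 1.96/√35 = 0.33 SD at n = 35. The bias is smaller than this, but a reported mean and SD would not reveal it.

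**Staff scores.** If m staff were pooled with n caregivers and differed from them by g, the mean would shift by g × m/(m + n). With assumed values of 10 staff, 30 caregivers and g = ±0.5 SD, the shift is ±0.5 × 10/40 = ±0.125 SD. The sign follows g, which the documents do not give. The text does not say whether the groups are pooled or separated.

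**The case against.** The strongest reply is that the plan already seeks these data. The scales are scheduled by visit. Sections 4.4, 7.4 and 9.3.1 pursue outcomes from families who stop, and Section 9.2 includes everyone. Section 10.1.5 allows questionnaires by phone or on paper, and Section 5.5 pays for each visit. The interview shares the endpoint column, so the request in Section 4.4 can be read to cover it. The phrase about completed coaching may be only a statement of timing, like the six-month point for staff in the same sentence. Session completion is reported, and reasons for withdrawal (Section 7.3) and for assessments not done (Section 10.1.5) are recorded.

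Most of this stands. It rules out a claim that AIM, IAM and FIM come from completers only, and it makes 0.15 SD per 1-SD gap the worst case. It does not settle the interview, because two sections say one thing and the Schedule with Section 4.4 implies another. Completion rates show how many families stopped, not how they rated the intervention.

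A reader might also infer that staff scores are pooled with caregiver scores and raise the mean. The documents do not say so. Staff sign a separate consent form and interview guides are tailored by stakeholder group, which points if anything towards separate treatment. Nothing shows that staff would score higher than caregivers.

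**Conclusion.** The interview provisions conflict and should be reconciled, and the scales lack a time point suited to families who leave early. An upward bias in acceptability and feasibility is possible. At the plan's own 15% attrition it runs from 0, if every stopper answers, to 0.15 SD for an assumed 1-SD gap if none does, with 0.07 SD if half do. The gap and the response share are assumptions.

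It would go too far to conclude that the scores will look better than enrolled caregivers found the intervention. The direction depends on stoppers scoring lower and the size on how many answer, and the documents give neither. Nor is measuring acceptability after the intervention a bias in itself. Silence on separate caregiver and staff summaries, and the mismatch over week-0 AIM, are points for clarification only. The change is still worth making: it is cheap, and it protects the evidence from about five families on the question the study asks.

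**What to change.** 1. In the interview entry of Section 8, in Section 9.3.2 and in the Schedule of Activities, replace the condition on completed coaching with: *at week 9, or when coaching stops for caregivers who leave early*. Offer AIM, IAM and FIM at the same point.
2. Beside the caregiver mean and SD for each scale, report the number answering over the number enrolled.
3. Record when each early stopper was assessed, and show results with and without them. This handles the small downside that their assessment falls at a different time from week 9.
4. As clarifications, state that caregiver and staff scores are summarised separately, and reconcile the schema's week-0 AIM with the Schedule.

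The cost is a few words in three places, and the same short survey and interview offered earlier to roughly five families. No new instrument is needed. The response counts and the separate summaries need no new data and can go into the final analysis plan that Section 9.3.1 requires before database lock. Imputing the lowest observed score for non-responders is a debatable choice and is not needed here.
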